8.3.7 Adverse Events of Special Interest (Not Applicable)

No AEs of special interest are defined for this study.

8.3.8 Medical Device Deficiencies (Not Applicable)

The medical device to be used in this study is a vibrating mesh nebulizer that is FDA-approved and CE-marked and is to be used per the manufacturer's recommendations. Therefore, data on device deficiencies will not be collected in this study.

8.4 Tokenization (Optional)

Tokenization is the process of converting a piece of data into a random string of characters known as a token. Tokenization protects sensitive data by substituting non-sensitive data. The token serves merely as a reference to the original data, but cannot be utilized to determine those values. The advantage of tokens is that there is no mathematical relationship to the real data that they represent. The real data values cannot be obtained through reversal, and hence, a breach renders the information invaluable. Tokens are being increasingly used to secure varying types of sensitive information. In particular, personal identifiable information such as healthcare information, email addresses and account numbers are such examples. From a security perspective, tokenization significantly reduces risk based on the fact that sensitive data cannot be breached if it is not there in the first place.

Tokenization applies only to US participants who agree and sign the optional ICF. The piece of personal data needed to generate the token will be collected to create a unique, de-identified token. This token would be instrumental to enrich and aggregate other study participants' data coming from different sources for the purpose of future research. The benefit of linking data in general, is that the data set that is created can be used to answer a variety of healthcare- and therapy-related questions that could not otherwise be answered through conventional means.

8.5 Treatment of Overdose (Not Applicable)

There is no risk of overdose.

8.6 Pharmacokinetics (Not Applicable)

Pharmacokinetic parameters are not evaluated in this study.

8.7 Pharmacodynamics (Not Applicable)

Pharmacodynamic parameters are not evaluated in this study.

8.8 Genetics (Not Applicable)

Pharmacogenomics are not evaluated in this study.

8.9 Biomarkers (Not Applicable)

Biomarkers are not evaluated in this study.

8.10 Medical Resource Utilization and Health Economics (Not Applicable)

Health Economics/Medical Resource Utilization and Health Economics parameters are not evaluated in this study.

9 Statistical Considerations

9.1 Statistical Hypothesis

RESP301 reduces the rate of progression in the modified WHO ordinal scale in COVID-19 (see Section 8.1.1).

The endpoint of worsening level on the WHO ordinal scale represents a composite endpoint of scales above the entry level, being (i) death (level 7), (ii) hospitalized, on invasive mechanical ventilation or ECMO (level 6), (iii) hospitalized, on non-invasive ventilation or high-flow oxygen devices (level 5) , or, for those patients who were recruited at WHO ordinal scale 3, (iv) hospitalized, requiring supplemental oxygen.

9.2 Sample Size Determination

A total of 300 hospitalized participants with confirmed COVID-19 will be randomized 2:1 to receive RESP301+SOC (200 participants) or SOC alone (100 participants).

The comparison between the treatment arms for the primary endpoint will have approximately 80% power and alpha level 0.025 (one-sided) to demonstrate significant reductions (15% versus 30%) of the primary endpoint between RESP001+SOC and the Control arm (SOC), a 50% relative reduction for the proportion of participants who progress by at least one level on the WHO ordinal scale (see definition of the primary endpoint).

Two interim analyses are planned (see Section 9.5 for details):

1. The first IDMC interim analysis will take place after the first 60 participants have completed Day 10 of the study to evaluate whether the study can be stopped for futility based on change from baseline in room air SpO₂. For a final decision to stop the study for futility the results on other endpoints will be considered as well.
2. The second interim analysis will take place after 150 participants have completed Day 14 post-randomization based on event rate for the primary endpoint. The purpose of the second interim analysis will be futility as well as a potential sample size re-estimation in case the actual results differ from the original assumptions.

In addition to the review of efficacy data, safety will be assessed at each of the interim analysis by the IDMC. Further details are provided in Appendix 5.

9.3 Populations for Analyses

For purposes of analysis, the following analysis sets are defined:

Table 9-1 **Populations for Analysis**

Population (Analysis Set)	Description
Intent-To-Treat (ITT) Population	
The ITT Population will include all randomized participants. The ITT participants will be analyzed according to randomized treatment, irrespective of the actual treatment received. Participants who withdraw from treatment early will be followed for the assessment of the Day 14 primary endpoint. All efficacy analyses will be performed using the ITT Population.

Per Protocol (PP) Population	
The PP Population will include all participants in the ITT Population with no major protocol deviations that may significantly impact data integrity or patient safety. The PP Population will be used for supportive analyses of the efficacy measurements.

Safety Population (SP)	
The SP will include all randomized participants who inhale any amount of study intervention or are randomized to the control arm. The SP will be analyzed according to the actual treatment received. This set will be used for the safety analyses.

The ITT Population will be the primary analysis set for all efficacy analyses and the PP Population will be used to demonstrate robustness of results for the primary efficacy endpoint.

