1.3 Schedule of Activities (SoA)

Table 1-1 Schedule of Activities (SoA)

Procedure	Screening (up to 48 hours before Day 1 ¹)	Intervention Period			Early withdrawal	Efficacy follow-up (Day 14) ² (± 2 days)	EoS efficacy and safety follow-up (Day 28) ² (± 2 days)	Notes
		Day 1 ¹	Daily while hospitalized	Day 10 / hospital discharge				
Informed consent	X							Optional tokenization ICF to be provided for a subset of participants in the United States (see Section 8.4)
Confirmation of COVID-19 infection by nasopharyngeal RT-PCR ³	X							
Inclusion and exclusion criteria	X	X						Recheck clinical status before 1st dose of study intervention
Demographics	X							
Physical examination including height and weight	X			X	X		X ²	Full physical exam and height only at screening

Procedure	Screening (up to 48 hours before Day 1 ¹)	Intervention Period			Early withdrawal	Efficacy follow-up (Day 14) ² (± 2 days)	EoS efficacy and safety follow-up (Day 28) ² (± 2 days)	Notes
		Day 1 ¹	Daily while hospitalized	Day 10 / hospital discharge				
Pregnancy test (urine)	X							All women, including women of childbearing potential and pregnant women, may be enrolled in the study. Pregnancy status should be recorded (see Section 8.3.5). Note: Only females of child bearing potential and pregnant females need to undergo a screening pregnancy test.
Medical history (includes substance usage)	X							History of substance usage or abuse to be recorded but is not exclusionary
Medication history	X							In the prior 3 months
Laboratory assessments (including liver chemistries) ⁴	X ⁴	X ⁴	X (Days 3 and 7 only) ⁴	X ⁴	X ⁴		X ^{2,4}	
12-lead ECG	X							After resting supine for approximately 5 minutes. QRS, QT, QTcF, PR, RR, rate
Vital signs ⁵	X	X	X ⁵	X	X		X	Within 15 minutes prior to study intervention administration

Procedure	Screening (up to 48 hours before Day 1 ¹)	Intervention Period			Early withdrawal	Efficacy follow-up (Day 14) ² (± 2 days)	EoS efficacy and safety follow-up (Day 28) ² (± 2 days)	Notes
		Day 1 ¹	Daily while hospitalized	Day 10 / hospital discharge				
Randomization		X						

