4.1 Overall Design

This is an open-label, randomized, multicenter, parallel group, concurrent, controlled study in hospitalized participants with COVID-19 (WHO ordinal scale level 3 or 4) using a sequential adaptive design to evaluate the efficacy and safety of RESP301 added to standard of care (SOC). Approximately 300 adult (male and female) participants will be consented and randomized 2:1 to the Investigational arm or the Control arm. Participants randomized to the Investigational arm will receive inhaled RESP301 (6 mL) administered using a vibrating mesh nebulizer TID for up to 10 days in addition to the standard of care (SOC) while participants in the Control arm will receive SOC alone.

The study will be divided into the following periods:

- Screening period: starts up to 2 days (48 hours) prior to and extends up to the day of treatment initiation (Day 1); Days -2, -1 and 1

- Intervention period: up to 10 days; Day 1 to Day 10
- Efficacy follow-up: Day 14 and Day 28 (± 2 days)
- Safety follow-up: 28 days after treatment initiation; with the participant being contacted by phone call, if not still hospitalized, on Day 28 (± 2 days)

After screening, eligible participants will be randomized to either RESP301+SOC or SOC alone on Day 1, and the study treatment will be initiated as applicable (Table 1-1). Screening and randomization may happen on the same day (Day 1).

An individual administration of study intervention will be stopped, and supplemental oxygen resumed if applicable, if threshold limits of SpO₂ 89% or heart rate 120 beats/min (or as indicated by the Investigator) are exceeded (see Section 4.2 and Section 8.1.2). However, the participant may continue with subsequent doses if the Investigator judges that the benefit / risk ratio remains positive. In this case, the instruction to continue should be duly recorded in the participant's hospital file and the subsequent nebulization should be closely monitored.

Inhalation of study intervention should be completed within 20 minutes. A staggered dosing approach will be used for the first 10 participants (and enrolment up to completion of the first IDMC safety review) to monitor tolerability and response to RESP301 (see Sections 6.1 and 9.6).

The study treatment will be permanently discontinued prior to 10 days if the participant:

- Improves to level 1 or 2 of the modified WHO ordinal scale;
- Progresses to a level > 4 of the modified WHO ordinal scale;

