6.1 Study Intervention Administered

[figure not shown]
Table 6-1 Study Intervention(s) Administered

Study Treatment	RESP301 + SOC
Intervention Name:	RESP301
Type:	Drug
Dosage Formulation:	Admixture for inhalation
Unit Dose Strength(s):	Delivered dose (62 mg) sodium nitrite (NaNO ₂) (6 mL of NO-generating admixture of 150 mM NaNO ₂ , 50 mM mannitol and 100 mM citric acid)
Dosage Level(s):	One 6 mL-inhalation TID (every 8 hours) with at least 6 hours between 2 consecutive doses.
Route of Administration:	Inhalation
IMP and NIMP:	IMP
Sourcing:	RESP301 provided centrally by the Sponsor.
Dosing Instructions:	A vibrating mesh nebulizer will be used to administer the RESP301, under the direction of the study physician. Treatment is to commence within 5 minutes of RESP301 preparation. For the first 10 participants (and enrolment up to completion of the first IDMC safety review) RESP301 will be administered by intermittent inhalation to monitor tolerability and response to RESP301. After reviewing safety data, the IDMC will decide whether the intermittent inhalation of RESP301 can be replaced by a continuous inhalation. Before initiating each RESP301 inhalation, supplemental oxygen, if being used, will be interrupted for a few minutes until SpO ₂ levels are stable. Depending on the extent of SpO ₂ decrease, the RESP301 inhalation may be initiated or supplemental oxygen may be resumed at the discretion of the investigator. After treatment initiation, in case of SpO ₂ decrease, RESP301 inhalation may be paused and supplemental oxygen resumed. If the participant is unable to tolerate nebulization without supplemental oxygen, nasal oxygen may be administered during nebulization.
Packaging and Labeling:	Study intervention will be provided as two separate vials: NaNO ₂ /mannitol (3 mL) and citric acid buffered to pH 5.4 (3 mL), which will be labeled as required per country requirement.

Staggered dosing approach for the first 10 participants:

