7.1 Permanent Discontinuation of Study Intervention

It may be necessary for a participant to permanently discontinue (definitive discontinuation) study intervention. If study intervention is definitively discontinued, the participant will remain in the study to be evaluated for the Day 14 and Day 28 safety follow-ups. See the SoA (Table 1-1) for data to be collected at the time of discontinuation of study intervention and follow-up and for any further evaluations that need to be completed.

Study intervention will be permanently discontinued prior to 10 days if the participant:

- Improves to level 1 or 2 of the modified WHO ordinal scale;
- Progresses to a level > 4 of the modified WHO ordinal scale.

Additionally, study intervention should be permanently discontinued in the following circumstances:

1. Discontinuation of study intervention for abnormal liver tests should be considered if the Investigator believes that it is in best interest of the participant. The development of alanine aminotransferase (ALT) $\geq 3 \times$ ULN and bilirubin $\geq 2 \times$ ULN or ALT $\geq 3 \times$ ULN and international normalized ratio (INR) > 1.5 , if INR is measured, which may indicate severe liver injury (according to Hy's Law), must be reported as an SAE and the study intervention discontinued.
2. If, as part of normal clinical follow-up, a clinically significant change in ECG is identified, the Investigators should exercise their clinical judgement to decide whether continuing study intervention administration is in the best interest of safety of the participant.
3. AE/SAE if the Investigator believes that it is in best interest of the participant, including the following:
 - Development of significant bronchospasm * or worsening of cough that is not tolerated by the participant and leads to immediate discontinuation of the nebulization.
 - Progressive COVID-19 requiring initiation of invasive ventilation or high flow oxygen.
 - Development of mHb level above 3%.

- Inability to safely continue receiving study intervention due to compromised respiratory status while off supplemental oxygen and receiving nebulized therapy (manifest by drop in SpO₂, increased respiratory rate or clinical other findings).

Refer to the SoA (Table 1-1) for data to be collected at the time of study intervention discontinuation and follow-up and for any further evaluations that need to be completed.

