9.4.5 Other Safety Analyses

All safety analyses will be performed on the Safety Population.

1. Safety and tolerability assessed by clinical safety laboratory measurements, physical examinations, vital signs, concomitant medications; cumulative incidence of AEs, SAEs and severe AEs
2. Incidence of participants unable to tolerate nebulization due to:
 - Reduction in SpO₂ to < 90%, unless well clinically tolerated according to Investigator's opinion
 - Other clinical signs of intolerance according to Investigator's opinion
3. Incidence of clinical bronchial hyper-responsiveness related to nebulization

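### The Safety Population keeps every control but only those RESP301 participants who inhaled, so events in never-dosed participants leave the active arm alone; the likely direction favours RESP301 and the size is probably small

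*Protocol*

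**What the plan says.** The text reviewed is the current protocol version, which enrols WHO grades 3 and 4.

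- Table 9-1 (Section 9.3) sets entry to the Safety Population: "The SP will include all randomized participants who inhale any amount of study intervention or are randomized to the control arm". It then fixes the arm for those in the set: "The SP will be analyzed according to the actual treatment received".
- Section 9.4.5 leaves no other basis for safety results: "All safety analyses will be performed on the Safety Population".
- Efficacy is handled differently: "All efficacy analyses will be performed using the ITT Population" (Section 9.3).
- Section 4.1 puts dosing after allocation: "eligible participants will be randomized to either RESP301+SOC or SOC alone on Day 1, and the study treatment will be initiated as applicable".
- In Section 6.1 (Table 6-1), oxygen, if in use, is interrupted before each inhalation. Depending on how far SpO2 falls, "the RESP301 inhalation may be initiated or supplemental oxygen may be resumed at the discretion of the investigator". Footnote 6 of the Schedule of Activities marks the oxygen-interruption and stabilisation steps as applying to the active arm only.
- Section 7.1 ends study treatment permanently when a participant "Progresses to a level > 4 of the modified WHO ordinal scale".
- Section 8.3.1 collects AEs and SAEs in both arms from consent, so events before the first dose are on record.

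**The concern.** The two arms enter the safety set by different rules. A control needs only to be randomized. A RESP301 participant must also pass a step after randomization that depends partly on respiratory status and partly on an investigator who knows the allocation. A RESP301 participant who never inhales satisfies neither half of the definition and is absent from the safety tables. A control with the same early course stays in, and reportable events count.

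If the never-dosed are sicker than average, removing them lowers the RESP301 event rate and leaves the control rate unchanged. What is at stake is the randomized comparison of AEs, SAEs, severe AEs, laboratory results and vital signs. In an open-label trial of a product that Section 2.2.3 calls first-in-man, that comparison should not rest only on a set that one arm must qualify for after randomization.

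**Working it through.** **What the plan supplies.** Section 9.2 gives 200 participants on RESP301+SOC and 100 on SOC. The protocol states no never-dosed rate, no expected AE rate and no link between non-dosing and outcome. There is therefore no stated figure to reproduce, and everything below apart from the arm sizes is an assumption shown over a range.

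**Step 1: who falls out.** A never-dosed RESP301 participant has not inhaled and was not randomized to control, so the entry rule excludes them. The sentence on actual treatment assigns an arm to people already in the set. It does not admit anyone.

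**Step 2: can non-dosing depend on prognosis?** Yes, in two ways. Inhalation can be withheld after an SpO2 fall off oxygen (Section 6.1). Reaching a level above 4 ends study treatment (Section 7.1), so a participant who gets there before a first dose would, by implication, not start. Controls face no equivalent hurdle to enter the set.

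**Step 3: size.** Let p be the true event risk, the same in both arms (no treatment effect), k the number never dosed of 200, and f the share of those k who have the event.

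Reported RESP301 rate = (200p − kf)/(200 − k)

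Drop = p − reported rate = k(f − p)/(200 − k)

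With p = 15% (30 events expected in 200):

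| k | Half have the event (f = 0.5) | All have the event (f = 1) |
|---|---|---|
| 1 | 29.5/199 = 14.8%, drop 0.2 points | 29/199 = 14.6%, drop 0.4 points |
| 4 | 28/196 = 14.3%, drop 0.7 points | 26/196 = 13.3%, drop 1.7 points |
| 10 | 25/190 = 13.2%, drop 1.8 points | 20/190 = 10.5%, drop 4.5 points |

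With no true effect, the k = 10 row gives relative risks against 15% of 13.16/15 = 0.88 and 10.53/15 = 0.70.

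**Step 4: sensitivity.**
- If f = p, the drop is zero for every k.
- If f < p, the sign reverses. With k = 10 and f = 0, the reported rate is 30/190 = 15.8%.
- For k = 10 and f from 0.5 to 1, the drop is 2.1 to 4.7 points at p = 10% and 1.1 to 3.7 points at p = 30%.

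**Step 5: early looks.** Section 9.2 has safety assessed at each interim analysis, and the first has about 40 and 20 participants (Section 9.5). If the same set is used there, 2 never-dosed participants who both have events change 6/40 = 15.0% to 4/38 = 10.5%.

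**The case against.** The strongest reply is that very few participants will never be dosed. The off-oxygen check is repeated before each inhalation, dosing is three times daily for up to 10 days, and a single inhalation of any quantity is enough to enter the set. Nasal oxygen may be given during nebulization, and level 3 entrants have no oxygen to interrupt. Exclusion criteria 1 and 2 remove those likely to escalate within 24 hours and those unable to receive nebulized treatment safely. All of this stands and points to a small k.

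A second reply is that early deterioration mostly does not reach the AE tables. Appendix 4 (Sections 10.4.1 and 10.4.2) excludes expected COVID-19 progression from AEs and gives death from progression as an example that cannot be an SAE. Section 8.3.6 treats fever, cough, dyspnea and asthenia as disease-related events unless certain conditions are met. This also stands and weakens the effect. It does not cover events that are unrelated to COVID-19 or worse than expected.

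A third reply is that exposed active participants plus all standard-of-care controls is a defensible safety set, and that Section 9.4.6 lets the SAP add analyses. An exposed set does suit drug-specific tolerability. But the protocol itself fixes this set as the basis for all safety analyses, so the asymmetry is not a detail left open.

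Four stronger readings are tempting, and the documents do not support them:

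- *The pre-dose recheck is a second hurdle in the active arm only.* The Schedule of Activities says "Recheck clinical status before 1st dose of study intervention" in the eligibility row for Day 1, the day of randomization. It does not say the recheck follows randomization. If it comes before, it acts on both arms alike.
- *Deteriorating participants disappear from the trial.* They do not. Progression and Day 28 mortality are analysed on ITT, and SAEs in undosed participants are still reported to the sponsor.
- *The nebulization-intolerance rate is understated.* A participant who fails the off-oxygen step has not been nebulized. Counting that failure would redefine the endpoint.
- *The bias can be set against the 15-point difference in Section 9.2.* That difference belongs to the primary endpoint, which this rule cannot touch.

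**Conclusion.** The asymmetry is real and is written into Table 9-1. It excludes participants from one arm only, by a step that can depend on prognosis and on an unblinded decision. The direction most likely favours RESP301, but that is an inference from the dosing rules. A reader might infer that the RESP301 safety profile will certainly look better. The documents do not show that, because the shift is zero when non-dosing is unrelated to risk and reverses when the never-dosed are at lower risk, as could happen with consent withdrawn before the first dose.

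The size is unknown and probably small: under half a point for 1 never-dosed participant, and up to 4.5 points for 10 who all have the event. Those figures rest on an assumed 15% event rate, assumed counts of never-dosed participants, and assumed event shares of one half and one. Only the safety comparisons are affected. This is a worthwhile, inexpensive improvement and does not threaten the efficacy conclusions.

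**What to change.** In Table 9-1 and Section 9.4.5:

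1. Add a between-arm summary of AEs, SAEs, severe AEs and deaths on all randomized participants by assigned arm, counted from randomization in both arms.
2. Report the number of RESP301 participants never dosed, with the reason and outcome for each.
3. Keep the existing dosed set for drug-caused events, nebulization tolerability and bronchial hyper-responsiveness.
4. Report failures at the off-oxygen step separately, leaving the tolerability endpoint as defined.

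The AE data needed are already collected from consent, and no dose, schedule or clinical rule changes. The cost is wording and a few extra tables. The one statistical drawback is that unexposed participants slightly dilute drug-caused event rates in the all-randomized summary. Showing the dosed set beside it offsets that, which is why the new summary should accompany the existing set and not replace it.
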